## 4.0 If this research is hypothesis driven, succinctly state the hypothesis:

Hypothesis 1a: Participants in the Mentoring Program will have significantly improved QOL compared to those in the Educational Activity group post-intervention and 6 months later.

Hypothesis 1b: Participants in the Mentoring Program will have significantly improved functioning in typical life activities (i.e., functional abilities) and better disease outcomes (e.g., less severe disease as measured via biomarker and standardized indices) post-intervention and 6 months later.

Hypothesis 2a: Parents in the Mentoring Program will have significantly improved QOL compared to those in the Educational Activity group post-intervention and 6 months later.

Hypothesis 2b: The QOL of the mentors will significantly improve from baseline to post-intervention.

Hypothesis 3: Parent and child self-efficacy, illness uncertainty, coping, social support and child perceived stigma will mediate relationships between mentoring and outcomes. Sex will be explored as a moderator.

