## Methods

### 1.0 \* Outline the major steps and methodologies in the clinical protocol(s).

**If necessary, include a description of any procedures being performed already for diagnostic or treatment purposes.**

**Clearly differentiate between these procedures:**

**Study Design:** This is a multi-site randomized controlled clinical trial in which 200 participants ages 10–17 years will be randomly assigned to the Mentoring Program or an “Educational Activity” comparison group, with baseline assessments occurring prior to randomization. Mentors and mentees are introduced and their relationship lasts 1 year. Follow-up assessments occur post-intervention (12 months after mentor-mentee introduction and 6 months later). Youth in the Educational Activity group will be yoked to those in Mentoring Program, and the timing of their follow-up assessments will correspond to their yoked peer, which is a design we have used successfully in three prior projects.

**Mentoring Program:** The Mentoring Program is based on our NIH-funded pilot study (R21), our previous focus group data, empirically-derived best practices, recommendations from our local BBBS, and information from national mentoring resources (MENTOR, [www.mentoring.org](http://www.mentoring.org)). The format consists of year-long, 1:1 mentor-mentee relationships with group self-management activities, a private program website, a parent support component, and mentor support. Mentors and mentees have weekly contact (e.g., text, phone), with in-person contact at least once a month. Group activities occur bimonthly. Educational activities alternate with “fun” activities that provide informal opportunities for learning self-management skills. Educational topics include nutrition, disease management, and school issues, and are taught by experts in each content area (e.g., dietitian, pediatric gastroenterologist).

Matching mentors and mentees is based on gender (same), age, geographical proximity, ethnicity, and interests if possible. Mentors and mentees are expected to have weekly contact (e.g., text, phone), with in-person contact 1 – 2 times per month. Mentors, mentees and parents of those ≤18 years sign an agreement that establishes the nature of the relationship and the expectations. Closure procedures, conflict resolution, grievance and relationship termination policies based on BBBS and MENTOR policies have been developed, and are in the Mentoring Program handbook given to participants.

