Follow-up assessments will occur post-intervention and 6 months post-intervention. School absences will be obtained from each child's school at the baseline and post-intervention assessments. Chart reviews will be conducted for disease and outcome information including number of relapses, number of hospitalizations, number of days hospitalized, number of procedures, number of clinic appointments scheduled, and clinic attendance ratio (number of appointments attended/number scheduled). Medications will also be recorded. Disease severity will be assessed via standardized measures of disease activity (Pediatric Crohn's Disease Activity Index or the Pediatric Ulcerative Colitis Activity Index), physician global assessment (PGA; overall assessment of current disease severity based physical examination and patient report, categorized into remission, mild, moderate or severe disease activity), and the biomarker of fecal calprotectin, a commonly used biomarker in IBD.

Stool will be collected at baseline and post-intervention for the fecal calprotectin, which will be analyzed at CCHMC by site co-I [name]. A stool collection kit will be mailed to participants prior to the study visit, with instructions to collect the stool sample within 24 hours of the upcoming visit. A reminder phone call will be made the day before. Research staff will transport the sample back to the hospital and send it to CCHMC.

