## **2.0 \* Identify the variables to be measured and how they will be statistically evaluated:**

Formal Analysis of our Primary Hypotheses: First, the two arms will be compared on all variables at baseline to determine if statistically significant differences are present. If differences are found on baseline measures, they will be examined as covariates in all statistical models of interest in exploratory analyses. Importantly, only the pre-specified covariates of baseline outcome variable, gender, and site will be included in the primary and secondary analyses. For comparing the

Mentoring Program to the Educational Activity group on pre-post change for our primary analysis, the baseline measure of QOL for youth with IBD along with the gender and site will be included as covariates in the primary analysis, regardless of the results of statistical tests for baseline group differences. The following repeated measures (RM) model, similar to an analysis of covariance (ANCOVA), will be employed,  $y_{it} = B_0 + B_1 \text{Time}_i + B_2 \text{Time}_i \times \text{Trti} + B_3 \text{Gender}_i + B_4 \text{Site}_i + e_{it}$ , where implicitly it is assumed that there is no main effect of  $\text{Trti}$ ,  $y_{it}$  is the QOL for youth  $i$  at time  $t$ ,  $\text{time}_i$  is coded as 0 for the pretest and 1 for the post-intervention measure, and the primary effect of interest is  $B_2$ , which corresponds to the difference between the groups on change in youth's QOL. In this RM model, the baseline measure of QOL for youth is constrained to have equal means across groups by assuming there is no main effect for  $\text{trti}$ . This constraint yields a statistical test for  $B_2$  analogous to the test of a treatment group main effect in an ANCOVA, controlling for baseline QOL. The main advantage of the RM model is that it can be estimated in SAS PROC MIXED using maximum likelihood estimation by treating  $\text{Time}_i$  as a repeated measures factor with two levels, whereas an ANCOVA model would require listwise deletion to account for missing data.

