Formal Analysis of our Secondary Hypotheses: The same approach and statistical models employed for our primary hypotheses will be used for our secondary hypotheses within Hypotheses 1, 2, and 3. The main difference between the precise models used will be (a) the specific outcome variable and (b) the time point, post-intervention or 6 month follow-up, employed to form the change score for the hypothesis of interest.

Formal Analysis of our Exploratory Hypotheses: For Hypothesis 1, the RM model specified in our primary hypothesis will be employed, with the exception that the only effect in the model will be a main effect of  $\text{Time}$ , and the model will only be employed within the Mentoring Program group, since mentors are only available within this study arm. For Hypothesis 2 contained within our exploratory aim, we will employ a longitudinal mediation model with multiple mediators. Specifically, the figure illustrates the model of interest for examining the indirect effects of Mentoring Program compared to Educational Activity on QOL at the 6 month follow-up via the pathway of social support measured at the intermediate time point between baseline and post-intervention. The advantages of longitudinal data to examine mediation models have been well-documented in the methodological literature, yielding a unique opportunity for us to test these pathways over time within an RCT. We will use Mplus 7.31 and its state-of-the-art bootstrapping procedures to statistically test parent and child self-efficacy, illness uncertainty, coping and social support as mediators for the outcome of interest both individually and simultaneously, the latter being useful for determining if a particular mechanism accounts for substantially more variance in the treatment effect. We will follow the guidelines specified for testing longitudinal mediation within Cole and Maxwell and MacKinnon. We will allow for the possibility of a residual direct effect within our models. This same general approach will be used to examine all our mediators. For Hypothesis 3, sex will be examined as a moderator of the treatment effect by examining the three-way interaction between sex, time, and treatment group, while also including all two-way effects and the main effect associated with sex, into the statistical model employed for the primary hypothesis.

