### 2.0 If applicable, provide a statistical sample size justification stated in terms of study power or confidence interval width.

Our power analysis is based on our primary hypothesis that the Mentoring Program will provide a significantly greater increase in QOL compared to the Educational Activity group from baseline to post-treatment. We use a Type I error rate of .05 to test this primary hypothesis. For examining statistical power, we assume an independent samples t-test is used to test this hypothesis with a minimum of 80% power to obtain a sufficient per group sample size ( $n$ ), which is assumed equal across groups. Consequently, the standardized mean difference is the effect size required to obtain power and sample size. Our primary analysis also allows for the inclusion of site, gender and the baseline measure of the outcome as covariates, which will allow for an  $n$  equal to or smaller than that reported here for the same level of statistical power.

The results of our pilot study are used to estimate effect size for our power analysis. We found a standardized mean difference of .52 on the QOL total scale when examining group differences in pre-post change. We found effect sizes of .52 and 1.08 on the functional disability score and on the QOL social scale respectively, thus generally illustrating that we should expect effect sizes in the medium to large range for the current R01. Our sample size of n=100 per group (mentoring vs. comparison) would provide 94% power for a medium effect size of d=.5 and more than 99% power to detect a large effect size of d=.8. Even with 20% attrition, we would still have 88% power to detect a medium effect size and over 99% power to detect a large effect size. Thus, our sample size of n=100 is sufficient for detecting treatment effects that we would expect.

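### With one follow-up per model, the repeated-measures analysis is close to a completers' ANCOVA, and the 6-month comparison ignores post-intervention QOL

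*Combined protocol and SAP*

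**What the plan says.** All references are to the Combined protocol and SAP.

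- **Methods 2.0, primary hypotheses.** The model has a time term, a time-by-treatment term (B2, the effect of interest), gender and site. There is no treatment main effect, so baseline means are equal by construction. Time is treated "as a repeated measures factor with two levels". The main reason given for this model is that it can be fitted by maximum likelihood, "whereas an ANCOVA model would require listwise deletion to account for missing data". Covariates in primary and secondary analyses are restricted to the baseline outcome, gender and site.
- **Methods 2.0, secondary hypotheses.** The same model is reused. What changes is the outcome and "the time point, post-intervention or 6 month follow-up, employed to form the change score for the hypothesis of interest".
- **Study Summary 4.0, Hypothesis 1a.** "Participants in the Mentoring Program will have significantly improved QOL compared to those in the Educational Activity group post-intervention and 6 months later".
- **Methods 1.0, Study Design.** The trial runs "with baseline assessments occurring prior to randomization".
- **Methods 1.0, Procedures.** Two outcomes have no 6-month value: "Stool will be collected at baseline and post-intervention for the fecal calprotectin", and "School absences will be obtained from each child's school at the baseline and post-intervention assessments".

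Methods 2.0 describes no imputation, auxiliary variable or missing-data sensitivity analysis for the comparison between arms.

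**The concern.** Two things follow from fitting baseline plus one follow-up at a time.

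First, the missing-data advantage claimed for the model is mostly absent. Maximum likelihood keeps a youth with a baseline score and no follow-up in the data set, but that youth carries almost no information about B2. The real gain is for youth with a follow-up and no baseline. For QOL these should be few, because baseline precedes randomization.

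Second, the 6-month analysis discards a score that the trial will have observed. Dropout that is at random given baseline and post-intervention QOL need not be at random in a model that contains only baseline and 6-month QOL. The sustained QOL effect is half of Hypothesis 1a, so a bias there would affect a named claim.

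**Working it through.** **1. The plan's own figures.** Sample Size Information 2.0 assumes a two-group t-test: "We use a Type I error rate of .05 to test this primary hypothesis". With d = 0.5, the noncentrality is d × √(n/2).

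- n = 100 per group: 0.5 × √50 = 3.54 on 198 df; two-sided power 94.0% (stated 94%).
- n = 80 per group (20% attrition): 0.5 × √40 = 3.16 on 158 df; two-sided power 88.2% (stated 88%).

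Both reproduce and are not in dispute.

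**2. Why the two-level model reduces to completers' ANCOVA.** Let y0 be baseline and y1 the single follow-up, with unstructured covariance. Leave out gender and site, and take baseline as complete. The likelihood factors into two parts:

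- y0 for everyone, with mean B0;
- y1 given y0, for those with a follow-up, with mean (B0 + B1) + B2·Trt + β(y0 − B0).

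B1 is free, so the second part has its own intercept and shares no constraint with the first. The estimate of B2 is the treatment coefficient from regressing y1 on Trt and y0 in completers. In 100 simulated trials of 200 youth with 20% of follow-ups missing, the largest difference between the two estimates was 4 × 10⁻¹⁴.

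Gender and site terms that are constant over time tie the two parts together slightly. The standard error ratio is then 0.996, and the estimates differ by 0.014 SD on average. If 2% to 5% of baselines were missing, the planned model's empirical SD would be about 3% to 4% below that of ANCOVA.

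**3. How the 6-month bias arises.** The documents give no correlations or dropout pattern, so these are assumptions: SD 1; correlations 0.5 (baseline–post), 0.7 (post–6 months) and 0.45 (baseline–6 months); equal effect at both follow-ups; 22% lost after the post-intervention visit (per arm; overall where both arms share the link); low post-intervention scorers more likely to leave in the arm with the link.

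The coefficient of post-intervention QOL in 6-month QOL, given baseline, is (0.7 − 0.45 × 0.5) / (1 − 0.5²) = 0.475 / 0.75 = 0.633. The bias is roughly 0.633 times the between-arm distortion in post-intervention QOL, given baseline, among those who stay. At slope 1 in the comparison arm only, that distortion is −0.144 SD, and 0.633 × (−0.144) = −0.09 SD.

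Two-point bias in SD, by log-odds slope of dropout per SD of post-intervention QOL:

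| Link between post-intervention QOL and dropout | 0.25 | 0.5 | 1 | 1.5 |
|---|---|---|---|---|
| Comparison arm only | −0.03 | −0.05 | −0.09 | −0.12 |
| Opposite directions in the two arms | −0.05 | −0.10 | −0.18 to −0.19 | −0.25 |
| Same in both arms, d = 0.5 | −0.005 | −0.01 | −0.03 | −0.05 |
| Same in both arms, no effect | about 0 | about 0 | about 0 | about 0 |

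A link in the mentoring arm only gives the same sizes with the opposite sign. The three-point model's bias was under 0.01 SD throughout.

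**4. Sensitivity to the assumptions.** At slope 1, with post–6-month correlations of 0.5 to 0.8 and losses of 15% to 25%, the one-arm bias is 0.05 to 0.13 SD. With the link in one arm at slope 1, it falls to about 0.04 SD at 10% loss and 0.02 SD at 5%. A separate set (correlations 0.6/0.5/0.7 in the order baseline–post, baseline–6 months, post–6 months; slope 0.7; 20% loss per arm) gave about 0.06 SD for one arm, 0.11 SD for opposite directions and 0.003 SD for the same link with equal loss.

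**5. Trial-level consequences.** 2,000 simulated trials per scenario, 100 per arm, 22% loss, link in the comparison arm only, gender and four sites in the model:

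| | Two-point | Three-point |
|---|---|---|
| Slope 1: type I error | 11.1% | 4.7% |
| Slope 1, d = 0.5: mean estimate | 0.41 | 0.50 |
| Slope 1, d = 0.5: power | 82% | 95% |
| Slope 0.5: type I error | 6.6% | 6.0% |
| Slope 0.5, d = 0.5: power | 88% | 96% |

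The Monte Carlo error of a type I rate is about 0.5 points, so the type I difference at slope 0.5 is within noise; the power difference is not. Under completely random loss there is no bias, and the three-point 6-month standard error is 4% lower. For the primary contrast with 20% missing at the post-intervention visit, the standard error falls by 0%, 2% or 4% if none, half or all of those families complete the 6-month survey.

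**The case against.** The strongest reply is that no planned result is shown to be wrong. Maximum likelihood does retain incomplete cases, as the plan says. A completers' ANCOVA is valid when dropout depends only on arm and the modelled baseline variables. The primary contrast is unaffected by later loss. That is all correct, and it keeps this point to an overstated rationale and the secondary 6-month analyses.

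On size, material bias requires post-intervention QOL to drive dropout differently by arm, and nothing in the documents shows this. The comparison arm also receives monthly calls, educational events and website access (Methods 1.0), and the 6-month assessment is online and paid (Recruitment and Retention Tools 5.0). The 22% loss all falls after the post-intervention visit, whereas the plan's only attrition figure is 20% overall. At 5% to 10% loss the bias is small: large-sample type I error at slope 1 in one arm is about 5.3% to 6.2%. These limits stand. So does the remark that the sign is unknown: loss of low scorers from the mentoring arm would inflate the effect rather than hide it.

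Exact equality with ANCOVA also needs an unstructured covariance, and the plan names no structure. Under compound symmetry the estimates differ by 0.004 SD on average, which changes nothing of substance.

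Finally, a three-level model alters the prespecified primary model for a gain of at most about 4% in standard error. That is fair. The main reason for the change is the 6-month contrast.

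**Conclusion.** The point holds. As specified, each model gives nearly the completers' ANCOVA result for B2 whenever baseline is complete, so the stated advantage over listwise deletion is largely not delivered for QOL. That conclusion is algebraic. The 6-month comparison leaves out observed post-intervention QOL and is biased if that score predicts later dropout differently by arm. The size is conditional: roughly 0.02 to 0.09 SD for a one-arm link at slope 1 as loss runs from 5% to 22%, about twice the 22% figure for opposite links, and little or nothing for a shared link. The direction depends on which arm loses its low scorers. The slopes, correlations and loss rates are assumptions. The primary post-intervention test and the stated power are not called into question. This is a robustness improvement that should be made to the 6-month analyses.

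**What to change.** For outcomes scheduled at baseline, post-intervention and 6 months, specify one constrained-baseline model with:

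- Time at three levels and an unstructured covariance;
- no treatment main effect, and a time-by-treatment term at each follow-up;
- gender and site as planned.

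The post-intervention contrast remains the primary test. The 6-month contrast from the same model tests the sustained effect. If the investigators prefer to leave the primary model untouched, using the three-level model for the 6-month contrasts alone would give the same protection there.

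Fecal calprotectin and school absences keep the two-level model, since they have no 6-month value. The rationale for maximum likelihood should be reworded to say what the two-level model does and does not recover. The SAP should also state that the three-level model does not protect against dropout that depends on unobserved 6-month scores.

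The cost is some SAP wording, a small change to the PROC MIXED code and three more covariance parameters (six instead of three). No new data are needed.

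### The sex-moderation model adds Sex × Treatment to a model with no treatment main effect, which relaxes the equal-baseline constraint and makes the interaction test less precise and, with 0/1 sex coding, dependent on the labels

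*Combined protocol and SAP*

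**What the plan says.** Methods 2.0, Formal Analysis of our Primary Hypotheses, gives a model with Time, Time × Treatment, Gender and Site. It has no treatment main effect, and the stated reason is that "the baseline measure of QOL for youth is constrained to have equal means across groups", so that the test of B2 behaves like an analysis of covariance. Time "is coded as 0 for the pretest and 1 for the post-intervention measure". The model is preferred because "it can be estimated in SAS PROC MIXED using maximum likelihood estimation", which keeps participants with missing data, and Time is also treated "as a repeated measures factor with two levels".

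Under Formal Analysis of our Exploratory Hypotheses, sex moderation is tested by entering the interaction of all three factors, "while also including all two-way effects and the main effect associated with sex, into the statistical model employed for the primary hypothesis". Treatment is not listed as a main effect, so it stays out. The plan does not say how Sex is coded, does not exempt Sex × Treatment, and does not say that the constraint is meant to be relaxed here. Study Summary 4.0 gives the status of the analysis: "Sex will be explored as a moderator".

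**The concern.** Sex, Time and Treatment have three two-way effects, and Sex × Treatment is one of them. It does not vanish at Time = 0, so it lets the arms differ at baseline, which the primary model rules out. Because the treatment main effect is still missing, the model is not hierarchical, and its meaning then depends on how Sex is coded.

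With 0/1 Sex, one sex gets a covariance-adjusted treatment effect and the other gets a change-score effect. An arbitrary label decides which is which. Other codings avoid that but give up more precision. At stake are the reproducibility and precision of a named exploratory test that has modest power in any case.

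**Working it through.** **The plan's own figures.** Sample Size Information 2.0 states 94% power for d = 0.5 with 100 per arm, and "Even with 20% attrition, we would still have 88% power to detect a medium effect size". A two-sided two-sample t-test at 0.05 gives 94.0% with 100 per arm and 88.2% with 80 per arm, so both figures reproduce. The plan gives no figure for the sex-moderation test.

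**What the extra term does at baseline.** I take Sex to be the Gender covariate of the primary model. With Time numeric and equal to 0, the only term in the literal model that contains Treatment is Sex × Treatment, with coefficient b. The baseline difference between arms is then:

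- Sex 0/1: zero in the sex coded 0, b in the sex coded 1.
- Sex −0.5/+0.5: −b/2 and +b/2, forced equal and opposite.
- Sex as CLASS: a separate free difference in each sex.

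The rank of the fixed-effects design (Site left out) agrees. It is 6 without the term, whatever the coding of Sex and Treatment. With the term it is 7 for numeric Sex and 8 for CLASS Sex.

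**Inputs for the size.** From the plan: 100 per arm and 20% attrition. Assumed, because the plan does not give them: two-sided 0.05, SD 1, equal sex split, baseline-to-post correlation ρ of 0.3, 0.5 or 0.7, and an illustrative interaction of 0.5 SD. Those lost are taken as seen at baseline only and kept by maximum likelihood. Per arm and sex this gives nc = 40 completers and nb = 10 baseline-only.

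**Formulas.** Variance of the treatment effect within one sex:

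- baseline constrained: Vc = 2(1−ρ²)/nc
- baseline free: Vf = 2[(1−ρ²)/nc + (1−ρ)²/(nc+nb)]

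Interaction variance: 2Vc without Sex × Treatment, Vc + Vf with it and 0/1 Sex, 2Vf with it and centred or CLASS Sex. At ρ = 0.5:

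- Vc = 2 × 0.75/40 = 0.0375
- Vf = 2 × (0.75/40 + 0.25/50) = 0.0475
- standard errors: √0.075 = 0.274, √0.085 = 0.292, √0.095 = 0.308

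| | ρ = 0.3 | ρ = 0.5 | ρ = 0.7 |
|---|---|---|---|
| SE without the term | 0.302 | 0.274 | 0.226 |
| SE with it, Sex 0/1 | 0.333 (+10.2%) | 0.292 (+6.5%) | 0.234 (+3.5%) |
| SE with it, centred or CLASS | 0.361 (+19.6%) | 0.308 (+12.5%) | 0.241 (+6.8%) |
| Power at 0.5 SD, without the term | 38% | 45% | 60% |
| Power, Sex 0/1 | 32% | 40% | 57% |
| Power, centred or CLASS | 28% | 37% | 54% |

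**Dependence on the label.** The z-statistics from the two 0/1 codings have correlation 2Vc/(Vc+Vf) = 0.82, 0.88, 0.93. From the bivariate normal, they disagree on p < 0.05 in 5%, 4%, 3% of trials with no interaction, and in 17%, 15%, 11% with a 0.5 SD interaction.

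A single case shows why. Take complete data, ρ = 0.5 and a chance baseline difference of 0.3 SD between arms in one sex, with post-intervention means held fixed. The interaction shifts by 0.30 SD if that sex is coded 1, and by 0.5 × 0.3 = 0.15 SD if it is coded 0.

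With a 60/40 sex split, the excess standard error under 0/1 coding is 8%, 5%, 3% or 12%, 8%, 4%, depending on which sex is coded 0.

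**Checks.** With complete data Vf/Vc reduces to 2/(1+ρ), that is 1.54, 1.33, 1.18, which matches a generalised least squares calculation. Maximum-likelihood simulation used an estimated covariance matrix, four sites and 2,000 trials per setting. It gave rejection rates of 5.0% to 6.0% with no interaction for every model. The two 0/1 codings disagreed in 5.9%, 4.5%, 3.4% of trials with no interaction and in 18.4%, 15.3%, 10.8% at 0.5 SD. Without the term, the estimate was the same to 1e-14 with Sex 0/1, Sex reversed, or Sex and Treatment both CLASS.

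**The case against.** The strongest objection is that the defect depends on how Time enters. The plan also treats Time as a two-level repeated factor. If Time is a CLASS variable in the fixed effects, the design has rank 8 with or without Sex × Treatment, so the term changes nothing. That stands, but in that case the primary model has also lost its constraint (rank 5 instead of 4), contrary to its stated purpose. The 0/1 coding and the stated constraint both support the numeric reading.

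It can also be said that including every lower-order term is conventional, and that relaxing the constraint is valid and only less efficient. That is fair for CLASS or centred Sex. It is not a defence of 0/1 Sex, where the result depends on an arbitrary label. Nor does the plan's sentence give a complete hierarchy, because the treatment main effect is missing.

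Finally, the stakes are low. The analysis is exploratory, and the loss shrinks as ρ rises: at ρ = 0.8 the excess is 2.2% or 4.3%. The test has only 38% to 60% power at 0.5 SD for ρ of 0.3 to 0.7 even without the term. A 0.5 SD interaction is as large as the whole treatment effect used for the sample size. All of this stands, and it keeps the point minor.

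**Conclusion.** The concern holds as a minor specification error. On the plan's stated 0/1 coding of Time, the sentence on sex moderation relaxes the equal-baseline constraint under every usual coding of Sex: in one sex with 0/1, by one shared parameter with centred coding, and in both sexes with CLASS. With 0/1 Sex the test is both dependent on the label and less precise; with the other codings it is only less precise.

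The loss of the constraint is algebraic and needs no assumed value. Its size, 3.5% to 19.6% on the standard error for ρ of 0.7 down to 0.3, rests on the assumed correlation, the equal sex split and 20% of participants being seen at baseline only. Bias and type I error are not at issue, and neither the test of B2 nor the stated 94% and 88% power is affected.

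**What to change.** Replace the list of terms with Sex, Time, Sex × Time, Time × Treatment, Sex × Time × Treatment and Site, leaving out both Treatment and Sex × Treatment. State that Sex is the Gender covariate of the primary model. State also that Time stays the numeric 0/1 variable in the fixed effects; a CLASS copy of Time can serve the repeated-measures covariance structure. Baseline means are then equal across arms within each sex, and the result does not depend on how Sex or Treatment is coded.

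If the authors do want to relax the constraint for this analysis, they should say so and add the treatment main effect as well. That removes the dependence on the label, at the larger CLASS-type standard error.

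In either case, report the treatment effect in each sex and their difference with a confidence interval. The cost is one term removed and a line or two of text. No extra data are needed, and the primary analysis does not change.
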